7.5. Secondary analyses

7.5.1. Mediation analyses

For each participant, we will compute the average daily energy intake in the larger portion condition minus average daily energy intake in the smaller portion size condition, referred below as the portion size effect (PSE).

We will first report and compare the individual measures of impulsivity, inhibition, portion size appropriateness, satiety responsiveness, plate clearing tendencies, perceived food insecurity, resource availability in childhood, food choice motives, and compensatory health beliefs for lower and higher SEP groups using means, standard deviations and T-tests. If we find individual differences for any of these measures between participants of lower and higher SEP, mediation analyses will be performed in order to examine the extent to which it mediates the effect of SEP on the PSE (**Figure 2**).

[figure not shown]

Figure 2. Mediation diagrams for the PSE. Indirect effect of SEP on the PSE through a mediator M = $c - c' = ab$.

The mediation will be tested by estimating the indirect effects of SEP on the PSE through all the potential mediators and testing their indirect effect using bias-corrected bootstrap. We will use the PROCESS macro (Model 4 – one mediator at a time and all together) in SPSS that provides asymmetric bias-corrected bootstrap confidence intervals for inference about the indirect effects using 5,000 bootstrap samples [38]. Mediation will be tested by determining whether or not the confidence intervals of the indirect effects estimates contain zero.

If we do not find evidence that the PSE is moderated by SEP or that our individual difference measures do not explain moderation by SEP, we will repeat the primary analysis replacing SEP with the individual measures, to examine whether any of the individual difference measures moderates the main effect of portion size on daily energy intake.

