4. PARTICIPANTS AND RECRUITMENT

4.1. Recruitment

Recruitment advertisements will be placed on social media (Facebook, Instagram, Twitter), online noticeboards (Gumtree, Call for Participants), and University of Liverpool (and other local universities') staff and students announcements and mailing lists. Flyers and posters will be distributed around the University of Liverpool campus, and if needed in local businesses and via letterbox drops in local residences with a particular focus on the most deprived areas based on the Index of Multiple Deprivation (IMD). Participants will be reimbursed for their time and expenses (£70 at the end of the study).

Recruitment will be stratified by highest educational qualification achieved or currently studying for as follows:

- 50% lower qualification levels

- No formal qualifications
- 1–3 GCSEs or equivalent
(*Level 1: first certificate; GCSE – grades 3, 2, 1 or grades D, E, F, G; level 1 award; level 1 certificate; level 1 diploma; level 1 ESOL; level 1 essential skills; level 1 functional skills; level 1 national vocational qualification (NVQ); music grades 1, 2 and 3*)
- 4+ GCSEs or equivalent
(*Level 2: CSE – grade 1; GCSE – grades 9, 8, 7, 6, 5, 4 or grades A*, A, B, C; intermediate apprenticeship; level 2 award; level 2 certificate; level 2 diploma; level 2 ESOL; level 2 essential skills; level 2 functional skills; level 2 national certificate; level 2 national diploma, level 2 NVQ; music grades 4 and 5; O level – grade A, B or C*)
- A level or equivalent
(*Level 3: A level; access to higher education diploma; advanced apprenticeship; applied general; AS level; international Baccalaureate diploma; level 3 award; level 3 certificate; level 3 diploma; level 3 ESOL; level 3 national certificate; level 3 national diploma; level 3 NVQ; music grades 6, 7 and 8; tech level*)
- 50% higher qualification levels
 - Certificate of higher education (CertHE) or equivalent
(*Level 4: certificate of higher education (CertHE); higher apprenticeship; higher national certificate (HNC); level 4 award; level 4 certificate; level 4 diploma; level 4 NVQ*)
 - Diploma of higher education (DipHE) or equivalent
(*Level 5: diploma of higher education (DipHE); foundation degree; higher national diploma (HND); level 5 award; level 5 certificate; level 5 diploma; level 5 NVQ*)
 - Bachelor or equivalent

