4.2. Inclusion criteria

- Female only
- UK residents, age ≥ 18
- BMI between 22.5 and 32.5 kg/m²; as approximately 70% of adults in England have a BMI within this range [25]
- Proficiency in English language
- Self-report liking each of the test foods

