7.2.2. Independent variables

Socioeconomic position (SEP) will be derived from highest educational qualification, coded as lower (1 = No formal qualifications; 2 = 1–3 GCSEs; 3 = 4+ GCSEs; 4 = A level) or higher (5 = Certificate of higher education (CertHE); 6 = Diploma of higher education (DipHE); 7 = Bachelor; 8 = Master’s degree; 9 = Doctorate).

Impulsivity. Items from the Barratt Impulsiveness Scale will be coded from 1 to 4. The higher the summed score for all items, the higher the level of impulsiveness (min. = 30, max. = 120). McDonald’s Omega will be calculated as an indicator of internal consistency.

Inhibition. For correct responses, the median reaction times (RTs) in incongruent and congruent trials will be calculated [53,54]. The difference in median RTs between incongruent vs congruent trials will be calculated [incongruent RT – congruent RT] = *The Stroop interference effect*. Higher scores indicate poorer response inhibition.

Portion size appropriateness. For each participant the average selected portion size will be calculated in kcal.

Satiety responsiveness. Items will be coded from 1: *strongly disagree*, to 5: *strongly agree* and their mean will be calculated. A higher score indicates a higher satiety responsiveness. McDonald’s Omega will be calculated as an indicator of internal consistency.

Plate clearing tendencies. Response options range from 1 to 5: 1 = strongly disagree, to 5 = strongly agree. Responses will be averaged. Higher scores indicate higher plate clearing tendencies. McDonald’s Omega will be calculated as an indicator of internal consistency.

Perceived food insecurity. Based on the recommendations of the authors of the questionnaire [55] responses to the 6 questions about food insecurity will be coded as affirmatives (i.e. “yes”, “often true”, “sometimes true”, “almost every month”, “some months but not every month”) and negatives (i.e. “no”, “never true”, “only 1 or 2 months”). Coding of food security is based on the number of affirmatives as follows: 0-1 = “food secure”, 2-4 = “food insecure without hunger”, 5-6 = “food insecure with hunger”. The responses “don’t know” and blank responses reflect missing data, which will be imputed following best practice guidance [55].

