7.4. Primary analyses

7.4.1. Confirmatory analyses

To be consistent with previous studies we ran investigating the effect of SEP on intended energy consumption (e.g [45]), the primary measure of SEP used in our primary analysis will be highest educational qualification (binary – lower vs higher).

A mixed ANOVA will be used to test the effect of portion size (categorical: larger, smaller; within-subject), SEP (categorical: lower (\leq A level), higher ($>$ A level), between-subjects), the interaction portion size*SEP on daily energy intake. If the interaction between portion size*SEP is significant the analysis will be stratified by SEP (\leq A level, $>$ A level) and two repeated-measures t-tests will be used to examine the effect of portion size (larger vs smaller) on daily energy intake in the two groups of participants separately. We will not correct for multiple comparisons as we specified a priori hypotheses.

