9.6. APPENDIX F: PERCEIVED RESOURCE AVAILABILITY IN CHILDHOOD

Instructions: Think about your childhood before age 12 and rate your agreement or disagreement with the following statements.

	Strongly disagree 1						Strongly agree 7
My family had enough money for things growing up.							
I grew up in a relatively wealthy neighbourhood.							
I felt relatively wealthy compared to others my age.							

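### Resource availability in childhood (before age 12) is tested as a mediator of adult educational SEP, which it precedes, so a common cause would be reported as mediation

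*Combined protocol and SAP*

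**What the plan says.** **Exposure.** In section 7.2.2, SEP "will be derived from highest educational qualification, coded as lower" or higher; section 7.4.1 makes this binary variable the primary SEP measure. Participants are adults (section 4.2: "UK residents, age ≥ 18"), and section 4.1 classifies them by the highest qualification they hold or are working towards.

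**Candidate mediator.** Resource availability in childhood is the mean of three items on family money, neighbourhood wealth and felt wealth (section 7.2.2, Appendix F). The instruction reads "Think about your childhood before age 12 and rate your agreement or disagreement with the following statements".

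**Analysis.** Section 7.5.1 compares nine listed measures between the SEP groups; the list ends with "perceived food insecurity, resource availability in childhood, food choice motives, and compensatory health beliefs for lower and higher SEP groups". For any that differ, "mediation analyses will be performed in order to examine the extent to which it mediates the effect of SEP on the PSE". The tool is stated: "We will use the PROCESS macro (Model 4 – one mediator at a time and all together) in SPSS". Mediation is declared when the bias-corrected bootstrap interval for the indirect effect excludes zero. Section 2 gives the matching hypothesis for the individual difference measures as a group. Neither place exempts the childhood measure or comments on its timing.

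**The concern.** A mediator must lie after the exposure and be changed by it. Resources before age 12 come before the highest qualification of someone aged 18 or over, so the first leg of the path, from SEP to the measure, is not available as a causal effect. The opposite direction is plausible: childhood resources may influence both education and eating. The rationale in section 1 points that way, since it presents childhood harshness as itself promoting eating without hunger.

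The two readings lead to different conclusions. Mediation would mean that education acts on the PSE through childhood resources. A common cause would mean that part of the SEP difference in the PSE reflects early-life background and not adult education. Explaining why the PSE varies with SEP is the trial's stated secondary objective, so the label matters to what is reported.

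**Working it through.** **1. The plan's own figure.** Section 7.6 gives N=46 from f=0.175, within-subject correlation 0.7, two conditions, alpha 0.05 and 85% power. With λ = f²·N·m/(1−ρ):
- N=46: λ = 0.030625 × 46 × 2 / 0.3 = 9.39. Noncentral F with 1 and 44 df gives power 0.850, and 46 is the smallest N that reaches 85%.
- N=60: λ = 0.030625 × 60 × 2 / 0.3 = 12.25, power 0.931.

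The figure reproduces. Nothing below changes it.

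**2. Time order.**

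| Role in Model 4 | Variable | Period it describes |
|---|---|---|
| X | Highest qualification, held or being studied for | Age 18 or over |
| M | Resource availability in childhood | Before age 12 |
| Y | PSE, larger minus smaller portion day | Study days |

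M precedes X, so the mediated effect through M is zero whatever the data show.

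**3. Why the test cannot reveal this.** Let a be the slope of M on X, b the slope of Y on M given X, c the slope of Y on X alone, and c' that slope given M. Least squares gives c = c' + ab exactly, so c − c' = ab in every data set. The identity is algebraic and does not depend on whether X causes M or M causes X.

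**4. Size of the spurious indirect effect.** Suppose that M differs by d SD between SEP groups, that Y = b·M + error with unit error SD, and that SEP has no effect of its own. Then c' = 0 and the expected indirect effect is d × b, the whole SEP association. The values of d and b are assumptions; the documents give none.

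| d | b | d × b | Mean simulated ab, N=46 / N=60 | Mean simulated c, N=46 / N=60 |
|---|---|---|---|---|
| 0.5 | 0.30 | 0.150 | 0.148 / 0.155 | 0.149 / 0.143 |
| 0.8 | 0.39 | 0.312 | 0.305 / 0.318 | 0.289 / 0.310 |
| 0.8 | 0.59 | 0.472 | 0.457 / 0.483 | 0.459 / 0.477 |

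**5. How often mediation would be declared.** The measure must pass the SEP-difference screen and its interval must exclude zero. Section 7 sets p<0.01 for secondary analyses, so the screen is run at 0.01. Section 7.5.1 does not state the interval level, so both are shown. Assumed: SEP gap 0.5–1.0 SD, correlation of the measure with the PSE 0.3–0.5, no effect of SEP itself.

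| Screen / interval | N=46 | N=60 |
|---|---|---|
| p<0.01 / 95% | about 10–69% | about 15–88% |
| p<0.01 / 99% | about 6–60% | about 11–83% |

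The low ends come from the 0.5 SD gap and the high ends from 1.0 SD with correlation 0.5. Endpoints move by a few points between simulation runs and with how the correlation is defined. As a check, the settings of step 4 with a 0.01 screen and a 99% interval gave 7–44% and 11–66%. With a 0.8 SD gap but no effect of the measure on the PSE, the rates were 1% and 2%. The declarations therefore come from the common cause.

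**The case against.** **SEP could be read broadly, to include childhood.** The plan does not do so. It operationalises SEP as qualification, and the SEP measures in section 5.2.16 and the alternatives in section 7.4.2 do not include childhood resources.

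**The score is a retrospective perception, completed at the final session, so present position could colour it.** This stands as a caveat on measurement. Coloured recall is not the mechanism that the plan sets out to test.

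**The arithmetic is still a valid account of how much of the SEP difference the measure statistically explains.** This stands. What is wrong is the causal label.

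**The rates rest on assumed effects and on one of nine measures.** This also stands. Section 2 could further be read as allowing mediation to be interpreted only when the PSE differs by SEP. On that reading, with a 0.01 screen and a 99% interval, the rates at the extreme settings (0.8 SD with correlation 0.3; 1.0 SD with 0.5) fall to 2–19% at N=46 and 4–34% at N=60. Section 7.5.1 does not state the condition. A lower frequency does not make the label right.

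**The moderator fallback in section 7.5.1 already uses the measure sensibly.** It does, but only if SEP moderation is absent or unexplained, and it leaves the mediation test in place.

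**A stronger reading is tempting.** A reader might infer that the primary portion size by SEP test is also falsely significant, or that its model must adjust for childhood resources. The documents do not support this. The primary hypothesis is that the PSE is larger in the lower SEP group, which is a group comparison. If childhood resources differ by SEP and drive the PSE, that group difference is real and detecting it is correct. The measure is itself socioeconomic, and section 7.4.2 deliberately limits adjustment to demographic variables that are not SEP-based. Adjusting for it would answer a different question.

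**Conclusion.** Wrong as written, for one measure in a secondary analysis. That the childhood measure cannot mediate adult qualification follows from the plan's own definitions and needs no assumption about effect sizes. The frequency of a mislabelled result does need such assumptions, and the wide ranges above should be read as illustration only. Harm arises only if the measure differs by SEP and is related to the PSE. The primary group comparison and the sample size of 46 to 60 are unaffected. The wording should be corrected before analysis, because afterwards a positive result would be hard to relabel convincingly.

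**What to change.** 1. In section 7.5.1, remove resource availability in childhood from the mediator set, both from the single-mediator models and from the joint model. Amend the mediation hypothesis in section 2 to match.
2. Keep it as a moderator of the portion size effect.
3. State that any attenuation of the SEP difference after accounting for it will be described as confounding or shared early-life background, and not as mediation.
4. Optionally, enter it as a pre-exposure covariate in a sensitivity run of the mediation models for the other measures, since it may also be a common cause there.

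Items 1 to 3 cost only wording and a shorter mediator list. Item 4 costs one degree of freedom per model. The measure is already in the final-session battery, so data collection, sample size and the primary model do not change.

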7. STATISTICAL ANALYSIS

All statistical analyses will be performed using SPSS (Version 26.0). The level of significance will be set at $p < 0.05$ for primary analyses and $p < 0.01$ for secondary analyses to account for multiple testing.

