7.6. Sample size

In a previous study that used the same basic methodology but investigated the PSE over a 5-day period [39], the main effect of portion size on daily energy intake was partial $\eta^2 = 0.41$ – considered a statistically large effect size. From other studies examining shorter time frames, the effect of portion size on energy intake is medium-sized [7, 57]. To be conservative we will power the present study to be able to detect a small to medium size main effect of portion size on daily energy intake ($f=0.175$, $p < .05$, 85% power, within-subject correlation of 0.7 conservatively estimated from [39]), resulting in a minimum sample size of 46 participants. As there is limited evidence on the size of moderating effect of SEP on portion size, this sample size also provides adequate power to detect the same small to medium sized portion size and SEP interaction (within-between-subject interaction) on energy intake. Due to on-going COVID restrictions there is uncertainty over recruitment rates and it may be plausible to recruit more participants into the study. If it is feasible in the time frame of the project, we will aim to recruit up to a further 14 participants, resulting in a final $N=60$. This decision will be made prior to conducting any data analyses. Increasing sample size by approximately 30% would address uncertainty for power analysis parameters (e.g. a smaller than

anticipated sized effect being observed in the study) by increasing power. Furthermore, empirical estimates of sample sizes needed for reasonable power (e.g. 80%) in mediation analyses indicate that a sample of ≈ 60 would be sufficient to detect mediation through pathways that are medium and above in statistical size using bias-corrected bootstrap tests [40].

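### Mediation is, on the natural reading of 7.5.1, run only for measures whose SEP difference is found in the same 46–60 women, so reported indirect effects are overestimated on average

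*Combined protocol and SAP*

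**What the plan says.** Section 7.5.1 (Mediation analyses) first reports each individual-difference measure "for lower and higher SEP groups using means, standard deviations and T-tests". It continues: "If we find individual differences for any of these measures between participants of lower and higher SEP, mediation analyses will be performed". The purpose given is to judge how far the measure concerned, referred to in the singular, carries the influence of SEP through to the portion size effect. The singular pronoun points to a decision taken measure by measure. The sentence does not define what counts as finding a difference, but 7.5.1 sits under Secondary analyses, and section 7 sets "p < 0.01$ for secondary analyses to account for multiple testing".

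The next paragraph of 7.5.1 speaks of estimating indirect effects through the full set of potential mediators, with PROCESS Model 4, singly and jointly. It does not say whether a measure that showed no SEP difference is still in that set. No adjustment for selection is planned.

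Section 7.6 gives "resulting in a minimum sample size of 46 participants", with up to 14 more if feasible (60 in total). It describes about 60 as "sufficient to detect mediation through pathways that are medium and above in statistical size". No numerical SEP difference is given for any mediator.

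**The concern.** With a binary SEP variable, the two-group t-test on a measure is the test of path a in the single-mediator model. Using it to decide whether the indirect effect is estimated keeps the samples in which the estimate of a is large and drops the rest. The product a×b is then reported as if nothing had been selected.

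The stated aim is a question of size: how far a measure mediates the SEP effect on the portion size effect (PSE). Two things are at stake. The indirect effects that appear in the report are too large on average, and true mediators with a moderate SEP difference will often have no indirect effect reported at all.

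**Working it through.** **Inputs.** N=46 and N=60 (section 7.6), split equally by education (section 4.1), so n=23 or 30 per group. Level p<0.01 for secondary analyses (section 7); p<0.05 is shown as the alternative reading. Two-sided tests are assumed. The true SEP difference d is an assumption: 0.5 SD as the central case, because section 7.6 targets medium pathways and above, with 0.3 and 0.8 SD as the range.

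**The plan's own figure.** With f=0.175, two measurements and correlation 0.7, the noncentrality is f²·N·2/(1−0.7) = 0.030625×46×2/0.3 = 9.39. Power is 0.8505 for the main effect and 0.8502 for the interaction, and 46 is the smallest N reaching 85%. The stated sample size reproduces.

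**Smallest difference that passes.** t(1−α/2, 2n−2)·√(2/n):

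- N=46: 2.015×0.2949 = 0.59 SD (p<0.05); 2.692×0.2949 = 0.79 SD (p<0.01)
- N=60: 2.002×0.2582 = 0.52 SD (p<0.05); 2.663×0.2582 = 0.69 SD (p<0.01)

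A measure with a true difference of 0.5 SD cannot pass with an estimate at its true size.

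**Why a×b inherits the bias of a.** The gate depends only on SEP and the measure. Given those two, and a correct linear model, the estimates of b and of the direct effect c′ remain unbiased. So the mean of a×b among gated samples, divided by the truth, equals the same ratio for a, whatever b is. Simulation agrees: the ratio for b is 1.00 with the gate.

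**Mean of the estimate of a, given that it passes** (normal approximation). With se=√(2/n), cut-off z·se and u=(z·se−d)/se, the mean is d + se·φ(u)/P, where P=1−Φ(u); the opposite tail is negligible. At p<0.01, d=0.5:

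- N=46: u=(0.760−0.5)/0.2949=0.88; P=0.189; mean = 0.5+0.2949×0.271/0.189 = 0.92; ratio 1.84
- N=60: u=(0.665−0.5)/0.2582=0.64; P=0.261; mean = 0.5+0.2582×0.325/0.261 = 0.82; ratio 1.64

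**Simulation with the t-test** (mean estimate divided by truth; probability of passing in brackets):

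| True difference | N=46, p<0.01 | N=60, p<0.01 | N=46, p<0.05 | N=60, p<0.05 |
|---|---|---|---|---|
| 0.3 SD | 2.89 (6%) | 2.58 (7%) | 2.40 (17%) | 2.15 (21%) |
| 0.5 SD | 1.84 (17%) | 1.65 (24%) | 1.58 (38%) | 1.42 (48%) |
| 0.8 SD | 1.27 (51%) | 1.17 (67%) | 1.15 (76%) | 1.08 (86%) |

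Without the gate the ratio for a×b is 1.00.

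**Share of individual estimates above the truth** (d=0.5, no direct effect, over both N and both levels): about 72–80% of gated a×b estimates if b=0.31, and 76–86% if b=0.39. Both values of b are assumed.

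**Proportion of the SEP effect explained.** Section 7.5.1 gives c−c′=ab, so the total effect is c′+ab and rises with a×b in the gated samples. With no direct effect, numerator and denominator rise together and the proportion stays at about 1.00 of its true value. With a true proportion of 50% (assumed), p<0.01 and d=0.5:

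- N=46: the total is inflated by (1+1.84)/2 = 1.42, so the proportion is inflated by 1.84/1.42 = 1.30
- N=60: (1+1.645)/2 = 1.32, and 1.645/1.32 = about 1.24

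**The case against.** The strongest objection is that the gate is not explicit. The conditional sentence does not mention significance, and the following paragraph can be read as modelling every listed measure once any one of them differs. If that reading governs, most of the selection disappears. This stands as a reason to reconcile the two sentences. It does not remove the point, because the conditional sentence, taken on its own words, restricts mediation to measures showing a difference.

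Second, 0.5 SD is an assumption, and it is the lower edge of what section 7.6 targets. Measures such as food insecurity and childhood resources are socioeconomic in nature and may differ more. At 0.8 SD and p<0.01 the inflation is 17–27%, and at 1.0 SD it is 6–12%. This also stands, which is why the range is shown.

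Third, measures that fail the gate are not hidden. Their means, SDs and t-tests are reported, and the last paragraph of 7.5.1 may bring them in as moderators of the PSE. That is correct, but it yields no indirect effect for them.

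Fourth, the plan decides on mediation by whether an interval contains zero, in a secondary analysis. That limits the importance, but the same section also asks how large the mediation is.

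A reader might go further and infer three things that do not follow. Not every reported indirect effect is too large: the bias is an average, and roughly 14–28% of gated estimates at 0.5 SD are at or below the truth. The proportion explained is not inflated by the same factor, because the total effect shifts in the same samples. And the gate does not itself raise the false-positive rate of the bootstrap test, since it only adds a condition.

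**Conclusion.** The point holds as a matter of average size. On the natural reading of 7.5.1, reported indirect effects are selected for a large path a. At p<0.01 and an assumed true SEP difference of 0.5 SD, they average about 1.84 times the truth at N=46 and 1.65 times at N=60 (1.58 and 1.42 if the gate is read as p<0.05). The factor falls quickly for larger true differences and rises for smaller ones. At p<0.01 the gate would also leave about 76–83% of measures with a true 0.5 SD difference without an indirect effect. The proportion explained is unaffected when there is no direct effect, and inflated about 1.24–1.30 times at p<0.01 when the true proportion is 50%.

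These figures rest on equal groups, normally distributed measures, a linear model and the assumed differences. The analysis is secondary and the primary result is unaffected. This is a cheap improvement.

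**What to change.** In 7.5.1, delete the conditional sentence. State that the single-mediator Model 4 will be fitted for every prespecified measure whatever its SEP t-test shows, and that every indirect effect will be reported with its interval, whether or not the interval excludes zero. Keep the SEP t-tests as description. Reconcile the sentence on the full set of potential mediators with this, including which measures enter the joint model.

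Reporting all of them is essential. Even without the gate, attending only to indirect effects whose two paths are both significant at 0.05 overstates them by about 59–90% (d=0.5, b=0.39, both assumed).

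The cost is a short edit and a few more PROCESS runs on data already collected. The downside is that about ten intervals are reported instead of a few, at the plan's secondary level. If every measure was always meant to be modelled, the edit simply confirms it.
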